Until 30 September 2017, 452 subjects have been exposed to tepotinib. 60 subjects of these were exposed to the tepotinib + gefitinib combination. Five studies have been completed; 3 of these were conducted as single dose studies in healthy subjects (EMR200095-002, EMR200095-007, and MS200095-0012; n = 79 subjects), and 2 as multiple dose studies in subjects with different solid tumors (EMR200095-001 and EMR200095-003; n = 161). In addition, 4 studies in subjects with hepatocellular carcinoma (HCC; EMR200095-004, EMR200095-005) or epidermal growth factor receptor (EGFR) mutated or c-Met mutated non-small cell lung cancer (NSCLC; EMR200095-006, and MS200095-0022) are ongoing. In the ongoing studies, subjects with HCC received tepotinib as multidose monotherapy, and subjects with NSCLC received either multidose tepotinib monotherapy or a multidose combination with gefitinib in Phase I or Phase Ib/II studies. Doses of tepotinib of up to 1400 mg daily in subjects with solid tumors (EMR200095-001) and up to 1000 mg daily in subjects with HCC (EMR200095-004) have been explored.

The 500 mg tepotinib single oral dose has been studied in previous studies with 36 healthy subjects in total (EMR200095-007: 12 subjects, MS200095-0012: 24 subjects, 2 single doses of 500 mg) and was well tolerated. A dose of 500 mg once daily is the recommended Phase II dose (RP2D). Refer to the Investigator's Brochure for further information about the nonclinical and clinical programs and the implemented Guidance for the Investigator.

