Based on the currently available nonclinical as well as clinical safety data, there is no objection against administration of single doses of tepotinib to healthy subjects. It is recognized that healthy subjects will not get benefit by participating in this study. However, this study will generate mandatory human data about the potential of drug-drug interaction (DDI) of a proton pump inhibitor (omeprazole) on the PK of tepotinib, which is of importance in the context of concomitant medication in tumor patients with hepatic impairment treated with tepotinib. This is basic information to safeguard the further clinical development of tepotinib in patients suffering from malignancies such as HCC. During the development of tepotinib, in all 3 studies performed in healthy subjects (n = 79), the subjects well tolerated a single or 3 doses of tepotinib (different dose levels up to 500 mg single dose). All treatment emergent adverse events (TEAEs) were mild to moderate, except one Grade 3 asymptomatic lipase elevation in 1 subject. TEAEs did not show a pattern across all 3 trials. No serious adverse events (SAEs) were reported and no subject died. No clinically significant findings regarding laboratory parameters, vital signs and ECG including corrected QT interval according to Fridericia (QTcF) values were noted.

Elevations in serum lipase and amylase are considered as identified risks for subjects administered tepotinib. These elevations were observed in 5 of 79 healthy subjects exposed to tepotinib and were mild to moderate in severity (exception: one Grade 3 lipase elevation) and without apparent dose dependency. All increases of serum amylase/lipase were asymptomatic and not associated with a pancreatitis.

Subjects enrolled in this study might be exposed to a risk, including pancreatic enzyme elevation. However, inclusion of healthy subjects is justified when the administration of tepotinib is limited to a single dose or short term multiple administrations that will be given under close monitoring conditions to reduce the risk for untoward effects.

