5.5.2 Withdrawal from the Trial

Subjects must be withdrawn from the study by the Investigator at any time for any of the following reasons:

- Subject withdrew consent
- Subject lost to Follow-up

- Participation in another clinical study
- Relevant adverse events (AEs), especially serious adverse events (SAEs), occur that do not justify the subject's continuation in the study
- Pregnancy
- Protocol noncompliance judged as significant by the Investigator and/or Sponsor
- Use of a non-permitted concomitant drug as defined in Section 6.5. However, any medications that are considered necessary for the subject's wellbeing (eg paracetamol up to 1500 mg per day) may be given at the discretion of the Investigator
- Subject is no longer able to participate for other medical reasons (eg surgery, intercurrent illness)
- Any other condition which to the opinion of the Investigator no longer justifies or permits a safe participation of the subject.
- Any of the following individual stopping criteria is met unless deemed unrelated to study drug(s) (IMPs) by the Investigator with alternate etiology identified:
 - Abnormal clinically relevant vital signs confirmed on 2 or more measurements (min. 5 minute intervals), including abnormal blood pressure
 - o hypotension defined as systolic < 80 mmHg and/or diastolic < 40 mmHg, or
 - o hypertension defined as systolic > 160 mmHg and/or diastolic > 100 mmHg
 - Abnormal clinically relevant ECG findings, including a corrected QT-interval (ad modus Fridericia; QTcF) > 500 ms or an increase in QTcF > 60 ms compared to baseline, confirmed on ≥ 2 repeat measurements
 - Marked increases in liver or renal parameters (ALT/AST $\geq 3 \times$ upper limit of normal range (ULN), total bilirubin $\geq 2 \times$ ULN), creatinine $> 1.5 \times$ (ULN) confirmed by ≥ 2 repeat measurements
 - Any clinically relevant symptom or sign which in the opinion of the Investigator and/or Sponsor warrants subject withdrawal

If a subject has failed to attend scheduled trial assessments, the Investigator must determine the reasons and the circumstances as completely and accurately as possible.

In case a subject should be withdrawn from the trial, the medical monitor and clinical trial leader at the Sponsor will be informed immediately.

If there is a medical reason for the withdrawal, appropriate medical care will be provided.

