Healthy subjects might experience asymptomatic elevations in serum lipase and amylase. Any elevation in serum lipase and amylase of Grade ≥ 3 will lead to the recording of an adverse event of special interest (AESI). The severity of these AEs should be defined based on clinical judgment of the Investigator and defined according to NCI-CTCAE Severity Scale.

7.4.1.5 Safety Reporting to Health Authorities, Independent Ethics Committees/ Institutional Review Boards and Investigators

The Sponsor will send appropriate safety notifications to Health Authorities in accordance with applicable laws and regulations.

The Investigator must comply with any applicable site-specific requirements related to the reporting of SAEs (particularly deaths) involving trial subjects to the IEC that approved the trial.

In accordance with ICH GCP, the Sponsor/designee will inform the Investigator of “findings that could adversely affect the safety of subjects, impact the conduct of the trial or alter the IEC’s approval/favorable opinion to continue the trial.” In line with respective regulations, the Sponsor/designee will inform the Investigator of AEs that are both serious and unexpected and are considered to be related to the administered product (“suspected unexpected serious adverse reactions” or SUSARs). The Investigator should place copies of Safety Reports in the Investigator Site File. National regulations with regards to Safety Report notifications to Investigators will be taken into account.

When specifically required by regulations and guidelines, the Sponsor/designee will provide appropriate Safety Reports directly to the concerned lead IEC and will maintain records of these notifications. When direct reporting is not clearly defined by national or site-specific regulations, the Investigator will be responsible for promptly notifying the concerned IEC of any Safety Reports provided by the Sponsor/designee and of filing copies of all related correspondence in the Investigator Site File.

For trials covered by the European Directive 2001/20/EC, the Sponsor's responsibilities regarding the reporting of SAEs/SUSARs/Safety Issues will be carried out in accordance with that Directive and with the related Detailed Guidance documents.

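### The individual stopping criteria in Protocol 5.5.2 set no limit for amylase or lipase, the laboratory risk that Protocol section 3 identifies, so re-dosing after a Grade 3 or higher rise is left to judgement

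*Protocol*

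**What the plan says.** **Stopping list.** Protocol 5.5.2 says a subject must be withdrawn when "Any of the following individual stopping criteria is met unless deemed unrelated to study drug(s) (IMPs) by the Investigator with alternate etiology identified". The numeric limits are:

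- systolic pressure below 80 or above 160 mmHg, or diastolic below 40 or above 100 mmHg;
- QTcF above 500 ms, or a rise of more than 60 ms;
- under "Marked increases in liver or renal parameters": ALT/AST at 3 x ULN, total bilirubin at 2 x ULN, creatinine above 1.5 x ULN, confirmed by at least two repeats.

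The list ends with a criterion that has no number: "Any clinically relevant symptom or sign which in the opinion of the Investigator and/or Sponsor warrants subject withdrawal". Amylase and lipase do not appear.

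**Risk statement.** Protocol section 3 says: "Elevations in serum lipase and amylase are considered as identified risks for subjects administered tepotinib". They occurred in 5 of 79 healthy subjects and were mild to moderate ("exception: one Grade 3 lipase elevation"). All were asymptomatic and none was linked to pancreatitis.

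**Other places that bear on these enzymes.**

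- 5.3.1: neither enzyme may exceed ULN at Screening. ALT/AST may reach 1.1 x ULN.
- 5.4: eligibility is rechecked on Day -1 of Period 1 only.
- 7.4.1.4: a Grade 3 or higher elevation "will lead to the recording of an adverse event of special interest (AESI"). SAP 15.2.3.1 lists these events.
- 7.4.3: a physician judges abnormal values, and major deviations are followed until normal or shown not to matter.
- 6.5.6 proposes no specific measures for particular adverse events, and 6.1 marks treatment-modification rules as not applicable.
- Section 3 sends the reader to the Investigator's Brochure and "the implemented Guidance for the Investigator".

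**The concern.** Each subject is due three tepotinib doses and gains nothing from them. The protocol justifies using healthy subjects by close monitoring, which protects most when a result has a stated consequence. Parameters for which section 3 reports no clinically significant finding in healthy subjects (vital signs, QTcF) have fixed stops. The parameter behind the only event above moderate severity in those studies has none. A volunteer slightly above ULN for lipase should not enter. An enrolled subject with a confirmed, asymptomatic Grade 3 lipase after dose 1 or 2 meets no stated limit before the next dose. What is at stake is the consistency of subject protection. The treatment comparisons are not at stake.

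**Working it through.** The plan gives no figure on this point to reproduce. The check has three parts.

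**1. Is a consequence for the next dose attached anywhere?** Reading 5.5.2, 6.1, 6.5.6, 7.4.1.4 and 7.4.3 of the protocol and section 15 of the SAP together, the Grade 3 trigger leads to recording, listing and follow-up. None of these sections says that the next dose waits or that the subject stops. The only routes to withdrawal are the judgement-based reasons in 5.5.2.

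**2. How many subjects might meet a stop?** Inputs, all from Protocol section 3: one Grade 3 lipase elevation in 79 healthy subjects, and "MS200095-0012: 24 subjects, 2 single doses of 500 mg", so at least 79 + 24 = 103 administrations. Intervals are exact (Clopper-Pearson) 95% limits.

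| Basis | Rate (95% limits) | Multiplier | Expected subjects or doses |
|---|---|---|---|
| Per subject, all 12 | 1/79 = 0.01266 (0.00032; 0.06852) | 12 | 0.152 (0.0038; 0.822) |
| Per subject, only doses followed by another (assumes equal risk after each dose) | same | 12 x 2/3 = 8 | 0.101 (0.0026; 0.548) |
| Per dose, doses 1 and 2 | 1/103 = 0.00971 (0.00025; 0.05291) | 12 x 2 = 24 | 0.233 (0.0059; 1.270) |

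The chance that at least one of 12 subjects has a Grade 3 elevation, at 1/79 per subject, is 1 - (78/79)^12 = 0.14.

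No row is a firm bound. The per-subject rate comes from subjects who mostly had fewer than three doses, so 0.152 may be too low here. Section 3 also says that some earlier subjects took three doses, so 103 is a minimum count and the per-dose figure may be too high. Whether the one event was confirmed on repeat, and at what dose it arose, is not stated.

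**3. Is there time to confirm?** Inputs: 14-day minimum washout between tepotinib doses (5.1); chemistry on Day -1, before tepotinib, and at 72 h discharge (Tables 2 and 3); PK visits at 96, 120 and 144 h.

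- Chemistry draws between consecutive tepotinib doses: 72 h, next Day -1, next predose = 3. Over two intervals: 3 x 2 = 6.
- 72 h sample to next tepotinib dose: 14 - 3 = at least 11 days.
- Day -1 to tepotinib: 5 days if B or C is next (Day -1 to Day 5, no Day 0), 1 day if A is next. Of 6 x 2 = 12 period transitions over the six sequences, A is next in 4 and B or C in 8.
- Tightest case, B or C next: Day -1 falls at least 14 - 5 = 9 days after the previous tepotinib dose. The 144 h visit is at 6 days, so all three ambulatory visits are over at least 9 - 6 = 3 days before admission.

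A Grade 3 result at 72 h can therefore be repeated twice, before omeprazole starts, at visits where blood is already drawn.

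**The case against.** The strongest reply is that the case is already covered. 5.5.2 is mandatory in form. Its catch-all reaches any clinically relevant sign, 7.4.1.1 counts an abnormal laboratory finding among such signs, and the catch-all names the Sponsor as well as the Investigator. An AESI record brings the event to attention under the adverse-event reason, and 7.4.3 requires follow-up. Even the numeric stops give way when an alternate cause is identified, and the vital-sign and ECG stops also require clinical relevance. Individual judgement is defensible for a rise that was asymptomatic and not linked to pancreatitis. The Investigator's Brochure may hold handling advice.

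Much of this stands and limits the weight of the point. It does not close the gap, because the same discretion also covered ALT/AST, creatinine and QTcF, and limits were set there. Follow-up under 7.4.3 does not say that dosing waits. The Brochure guidance cannot be seen here, and the stop list does not refer to it.

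A reader might infer that a subject with Grade 3 lipase could not be withdrawn, or would have to be re-dosed. The documents do not support that: withdrawal is available, only without a stated limit. Nor do they show that no handling guidance exists.

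Two limits of the remedy also stand. A rise that normalises on repeat would not stop the subject. And the trigger is a grade, which 7.4.1.4 bases partly on the Investigator's clinical judgement.

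**Conclusion.** The point holds as an inconsistency in subject protection: fixed stops for five parameters, none for the named laboratory risk, and re-dosing in Periods 2 and 3 decided by judgement. The gain from closing it is modest. Roughly 0.1 to 0.2 of 12 subjects would be expected to meet the stop, with 95% limits running from about 0.003 to 1.3 across the counting bases. All of this rests on one event, on mixed earlier dose levels, and on those rates carrying over to this trial. It would be wrong to read 0.15 as a ceiling, since the per-dose count gives 0.23. It would also be wrong to infer a threat to the primary analysis: the C/A and C/B estimates are unaffected. This is a cheap improvement worth making.

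**What to change.** Add one bullet to the individual stopping criteria in Protocol 5.5.2: *Amylase or lipase elevation of NCI-CTCAE Grade ≥3 confirmed by ≥2 repeat measurements.* The existing alternate-etiology exception applies. Add one sentence: *After a Grade ≥3 amylase or lipase result, the next period does not start until the repeat results are available.* Cross-refer to it from 7.4.1.4, and adjust the statement in 6.1 that treatment-modification rules do not apply.

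For a 72 h result, the repeats can be drawn at the 96, 120 and 144 h visits, with subjects attending fasted as 7.4.3 specifies. No repeat omeprazole course is needed for this core rule. A rise first seen in the predose sample falls inside a period already begun and would stay with the judgement-based reasons. Laboratory turnaround is not stated; the rule assumes that discharge and Day -1 results are reported before the next step.

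Costs:

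- **Blood.** The Appendix II total is 51.7 + 29.7 + 126.0 + 4.0 = 211.4 mL. Two biochemistry repeats add 2 x 4.7 = 9.4 mL, giving 220.8 mL. If a delayed start also meant repeating one Day -1 panel (4.7 + 2.7 = 7.4 mL), the total would be 228.2 mL. Both are below 250 mL.
- **Conduct.** A period may occasionally be delayed. The 14-day washout is a minimum, so this is not a deviation from it. A withdrawn subject with incomplete PK data is already to be replaced, at the small expected number above.
- **SAP.** None: section 9 already flags repeat laboratory values and, as a rule, leaves them out of summary tables.

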6.3 Assignment to Treatment Groups

Subjects will be randomly assigned to one of six treatment sequences (see Section 8.2). Only subjects who comply with all selection criteria will be included into the trial. Prior to the first administration the subjects will be assigned to a treatment sequence via the random number on Day 1.

According CRO standard operational procedures (SOPs) the subjects will be assigned to the random number in the order of their registration to the study (first registration results in the lowest available random number, second registration results in the second lowest available random number, and so on). However, precedence will be given to subjects who participate in a trial at **PI** for the first time and for subjects who served as “stand-by” during a preceding trial.

The Investigator will keep a record relating the subjects' random numbers and the names of all subjects (including screening number and the Nuvisan GmbH ID number) who have given their informed consent, to allow easy checking of data in subject files, when required. This record will also include the date of subject's enrolment and completion, as well as subjects who could not be randomized for whatever reason.

6.4 Non-investigational Medicinal Products to be Used

Not applicable.

6.5 Concomitant Medications and Procedures

All concomitant medications taken by the subject during the trial, from the date of signature of informed consent are to be recorded in the appropriate section of the eCRF, noting the name,

dose, route, duration, regimen, status and indication of each drug. Nondrug interventions and any changes to a concomitant medication or other intervention should also be recorded in the eCRF.

6.5.1 Permitted Medicines

Paracetamol is the only permitted medication. Paracetamol will be permitted up to a maximum daily dosage of 1500 mg.

Any medications that are considered necessary to protect subject's welfare and that will not interfere with the IMPs may be given at the Investigator's discretion. The potential DDIs with tepotinib are still under evaluation. Therefore, medically required concomitant medication might have to be adjusted based on tolerability and the clinical response.

The Investigator will record, in the appropriate section of the eCRF, all previous/concomitant medications taken by the subject during the trial, from the date of signature of informed consent.

6.5.2 Prohibited Medicines

The following treatments and therapies are not permitted during this trial:

The subjects are prohibited from using prescription or over-the-counter medications (apart from paracetamol up to 1500 mg per day, as judged appropriate by the Investigator) within 14 days or 5 half-lives, whichever is longer, prior to the first IMP administration during the trial, and until after the End of Trial Visit.

6.5.3 Permitted/Prohibited Procedures

Subjects should drink about 2 L fluids per day during the hospitalization phase and will be reminded regularly.

Throughout the PK profiling days, the following restrictions must be met:

- Subjects will be fasting for at least 10 h before administration of tepotinib (except for the breakfast in Treatments A and C) and before administration of omeprazole
- Drinking is not allowed 1 h after administration of tepotinib
- Chewing gum is not allowed during the PK profile days.

Throughout the study, the following restrictions must be met:

- No smoking or use of tobacco products
- No alcohol intake
- No intake of food or beverages other than that provided to the subjects by the CRO during the inpatient period

- No intake of caffeine- and xanthine-containing food and beverages (eg coffee, black or green tea, chocolate or chocolate-containing food or beverages) from 48 h before administration of tepotinib in each period until collection of last PK blood sample of each period
- No intake of herbs/fruits that can have an influence on PK (eg St. John's Wort, Seville oranges, grapefruits, cranberry or the juice of these fruits), from 14 days prior to Day -1 of Period 1 until final examination
- No intake of concomitant medication within 14 days or 5 half-lives, whatever is longer, before first administration of study drug until final examination (except for paracetamol up to 1500 mg per day, may be given at the discretion of the Investigator)
- No intake of recreational drugs within 14 days or 5 half-lives, whatever is longer, before first administration of study drug until final examination
- No exhausting physical activities (body building, sports) from at least 72 h before the first administration of study drug until the final examination
- No sun baths, solarium or sauna at least 12 h before first administration of study drug until final examination.

6.5.4 Other Interventions

Not applicable.

6.5.5 Special Precautions

Not applicable.

6.5.6 Management of Specific Adverse Events or Adverse Drug Reactions

No specific measures are proposed at this stage. Standard medical care will be provided at the trial site for all AEs occurring during the trial.

6.6 Packaging and Labeling of the Investigational Medicinal Product

All IMPs will be packaged and labeled in accordance with all applicable regulatory requirements and Good Manufacturing Practice Guidelines.

The investigational product tepotinib will be provided by the Sponsor packed in alu/alu blister.

Omeprazole will be purchased from commercially available supplies.

6.7

Preparation, Handling, and Storage of the Investigational Medicinal Product

The pharmacy or designee will receive the IMPs labeled and packaged according to the local regulatory requirements and the storage requirements. Tepotinib and the interaction drug will be supplied in ready to use oral formulations. The responsible pharmacist will dispense the necessary amount of the IMPs. Detailed guidance will be provided in an IMP handling manual.

The IMP supplies will be recorded in an IMP inventory.

Tepotinib must be carefully stored at the trial site in a closed room or cabinet with restricted access, safely and separately from other drugs and protected from environmental extremes until used in the trial. Tepotinib should be stored at or below 25°C. Any deviations from the recommended storage conditions should be immediately reported to the Sponsor, and the IMP should not be used until authorization has been received from the Sponsor. The preparation, handling and storage of the IMP will be documented.

Detailed recommendations for the use and storage of omeprazole are described in the Summary of Product Characteristics.

The IMPs must not be used for any purpose other than the trial in question.

It must be ensured at the trial site that the IMPs are not used after the use-by date. This is to be closely monitored by the responsible monitor.

6.8

Investigational Medicinal Product Accountability

The Clinical Trial Supply Department of Nuvisan GmbH is responsible for ensuring IMP accountability, including reconciliation of drugs and maintenance of records. Drug accountability will also be confirmed by the Trial Monitor.

- Upon receipt of IMPs, the responsible person will check for accurate delivery and acknowledge receipt by signing or initialing and dating the appropriate documentation and returning it to the location specified. A copy will be archived for the Investigator Site File
- IMP dispensing will be recorded on the appropriate drug accountability forms so that accurate records will be available for verification at each monitoring visit
- Trial site IMP accountability records will include the following:
 - Confirmation of IMP receipt, in good condition and in the defined temperature range
 - The inventory of IMPs provided for the clinical trial and prepared at the site
 - The use of each dose by each subject
 - The disposition (including return, if applicable) of any unused IMP
 - Dates, quantities, batch numbers, kit numbers, expiry dates, formulation (for IMP prepared at the site), and the individual subject trial numbers.

The Investigator site should maintain records, which adequately document that subjects were provided the doses specified in this protocol, and all IMPs provided were fully reconciled.

Unused IMP must not be discarded or used for any purpose other than the present trial. No IMP that is dispensed to a subject may be redispensed to a different subject.

A Trial Monitor will periodically collect the IMP accountability forms.

At the conclusion or termination of this trial, all used and unused IMP kits will be destroyed at the trial site according to local regulations and institutional guidelines. All used and unused medications will be carefully recorded and documented before destruction.

